6.3.1 Power for technical success

If the analysis of the above one-sided hypothesis test for p_{RFA} for an ablative margin of 3mm is conducted using Fisher's exact test, then with a sample-size of 62 lesions and allowing a type I error of 0.05, we can detect a value of $p_{RFA} > 0.161$ with 80% power. That is, the minimal detectable p_{RFA} difference is 0.103. Subgroup analyses (e.g., based on treated tumor size) will require larger effect sizes to retain the same level of power. However, the study is only intended to be powered for the primary analysis.

6.4 Statistical analysis of clinical success

It has been noted in the literature that if a tumor reoccurs in the same site, it typically does so within the first two years [4]. There is some evidence of reoccurrence as far out as 40 months but that is based on limited data and beyond 4 years there is no follow-up data [4]. For the purpose of this study, the analysis of the clinical outcome will be based on a 2-year endpoint. As with the determination of technical success,

a literature-based benchmark will be used in lieu of a concurrent control. Results in [5] suggest that the cumulative incidence of reoccurrence by 2 years is around 26.4% and by 4-years is around 37.8%. However, these results were not stratified by tumor size, which is known to be a very strong predictor of clinical success. In [4], reoccurrence rates of 14.1%, 24.5%, and 58.1% were reported for the small, medium and large tumor groups. However, these rates were evaluated over variable lengths of follow-up. The proportion of cases expected in the small, medium, and large categories are 12.9%, 41.9%, and 45.2% respectively (based on past clinical experience). The benchmark number to be used for the overall group comparison is the weighted average of these proportions with the above recurrence rates, which equals 24.1%. Because the failure rate data in [4] involve 1817 observations, we use this number as a basis for quantifying the precision in the baseline. Computing the lower end-point of a 95% confidence interval, we obtain $q_{\text{base}} = 0.2217$ as our ideal or most conservative benchmark against which to compare outcomes under PGP. This value is conservative even beyond the buffer provided by the allowance for uncertainty in its true value via the confidence interval end-point calculation as the follow-up times in [4] were shorter on average than 2-years.

For both the conservative and less conservative benchmarks, the overall assessment of the clinical success of PGP will be evaluated using the hypothesis test:

$$H_0: q_{\text{RFA}} \geq q_{\text{base}} \text{ against the alternative } H_1: q_{\text{RFA}} < q_{\text{base}}$$

where q_{RFA} is the probability of reoccurrence by 2-years of follow-up.

Patients are enrolled in the study over a 2-year period. Therefore, if every patient was followed up for 2-years, the study would be 4-years long. We propose a statistical analysis plan which will allow estimating the clinical performance of the PGP at any point after the initial recruitment phase of 2 years – with increasing accuracy as the analysis approaches the 4-year mark, having access to 2-year follow up data for each patient who entered the study.

The analysis will be as follows: the investigators will check the status of patients every 6-months (data may be available every 3-months for some patients but to be safe we only assume 6-month interval data will be available) and essentially impute future status from patients' prior status. The imputations will be automatically performed by a Bayesian analysis, which assigns an unknown parameter to each participant's 6-monthly future status, through 2-years of follow-up.

The data for each patient is a 5-item multinomial random variable indicating whether they experienced recurrence before 6-months, between 6 and 12 months, between 12 and 18 months, between 18 and 24 months, or survived recurrence-free to 24 months and a covariate for the size of tumor. The four values of the multinomial outcome variable are (1,0,0,0,0) for recurrence before 6 months, (0,1,0,0,0) for recurrence between 6 and 12 months, (0,0,1,0,0) for recurrence between 12 and 18 months, (0,0,0,1,0) for recurrence between 18 and 24 months, and (0,0,0,0,1) for no recurrence in the 24-months follow up period.

We refrain from using a Cox model or a parametric survival model to compare the status of the patients at two years of follow-up because reoccurrence status may only be known at 6-monthly intervals. Instead, we use a discrete-time survival model in which we model the probability of reoccurrence in each 6-month period thru 2-years of follow-up along with the event that the length of follow-up without reoccurrence exceeds 2-years. The dependent variable is a polytomous multinomial random variable because each patient's reoccurrence status (if followed up for the full 2 years) will be in exactly one of the 5 categories. The probabilities for the 5 categories sum to 1. The purpose of modeling the interim survival probabilities is that the interim probabilities allow the missing outcome status for patients not followed for two-years to be internally imputed during Bayesian model estimation. This approach allows for maximal use of the information in the data as all subjects are used in the analysis even if that haven't been followed up for two years (emulating what the Cox or other survival model does with continuous-time follow-up data). If we end up measuring reoccurrence status every three months, we will still pursue the described approach (but have 9 categories for the multinomial outcome as opposed to 5 categories) as the data will still not be close enough to continuous to support using the Cox model.

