6.2 Statistical Design

A single-arm trial of the research PGP computer technology is proposed in which a comparison of outcomes is made to benchmarks based on prior studies. There are two primary outcomes, technical success and clinical success. Because the measurement process is drastically different for these outcomes, the statistical analysis also differs markedly for each outcome and so each is separately described. Results from Kim, et al. [5] provide the benchmark against which the *technical* success of PGP is assessed. Results from Mulier, et al. [4] provide the benchmark against which the *clinical* success of PGP is assessed. We will recruit patients with a tumor size $>2\text{cm}$, and we will categorize tumor size as small if $< 3\text{cm}$, medium if between 3cm and 5cm , and large if $> 5\text{cm}$. In our analyses for clinical outcomes, we will weight our sample to equate to the relative frequencies of small, medium and large tumors to ensure that the new trial data is relevant to the benchmark from the historical data [4]. In addition to performing overall analyses and statistical tests, we will also report estimates broken down by tumor size and other subgroups of interest.

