6.4.2 Model for multinomial outcome: generalized logistic regression

The distribution of y_i is multinomial with five categories:

$$y_i | \theta_i \sim \text{Multinomial}_5(1, \theta_i)$$

where $\theta_i = (\theta_{i0}, \theta_{i1}, \theta_{i2}, \theta_{i3}, \theta_{i4})$ is the vector of probabilities associated with the five possible outcomes for patient i . Models for multinomial outcomes are characterized by the way in which the elements of θ_i are mapped to the predictors. One commonly used specification is generalized logistic regression in which each component of θ_i is compared to all other components through a logit link function by supposing:

$$\theta_{ik} = \lambda_{ik} / (\lambda_{i0} + \lambda_{i1} + \lambda_{i2} + \lambda_{i3} + \lambda_{i4})$$

and $\log(\lambda_{ik}) = \gamma_k + \beta x_i$ for $k = 0, \dots, 4$. A key feature of this specification is that the Bayesian software package JAGS will impute any y_{ik} whose value is missing. To implement this feature any values of y_{ik} that are missing will be represented as NA in the analytic data set. We note that the above specification assumes the proportional odds assumption that the effects of all terms other than γ_k does not depend on k holds. This is an assumption whose legitimacy can be tested empirically.

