6.4.4 Evaluation of hypothesis test and other summaries of the posterior distribution

We wish to average the 2-year survival probability across the study patients, given by

$$q_{\text{RFA}} = 1 - n^{-1} \sum_{i=1}^n \theta_{i4}$$

where based on the above generalized logit model the probability of clinical success at 2-years for patient i is given by

$$\theta_{i4} = \frac{\exp(\gamma_4 + \beta x_i)}{\exp(\gamma_0 + \beta x_i) + \exp(\gamma_1 + \beta x_i) + \exp(\gamma_2 + \beta x_i) + \exp(\gamma_3 + \beta x_i) + \exp(\gamma_4 + \beta x_i)}$$

The posterior probability of clinical success, $\Pr(q_{\text{RFA}} < q_{\text{base}} | y_1, \dots, y_n, x_1, \dots, x_n)$, is then determined by evaluating q_{RFA} for a large number of draws from the posterior distribution of the model parameters and evaluating the Monte-Carlo average

$$\Pr(q_{\text{RFA}} < q_{\text{base}} | y_1, \dots, y_n, x_1, \dots, x_n) \cong n^{-1} \sum_{j=1}^{n_{\text{sim}}} I(q_{\text{RFA}}^j < q_{\text{base}})$$

where q_{RFA}^j denotes the value of q_{RFA} computed on the j th of n_{sim} draws of the model parameters from their joint posterior distribution. The mean, standard deviation, and 95% interval estimates of q_{RFA} will be similarly determined.

Because the chance of clinical success likely varies continuously with tumor size, we can substitute the mean tumor size for the benchmark population in [4] for x_i to essentially control for tumor size. Alternatively, we may substitute x_i with the corresponding small, medium, and large tumor size subgroup mean and in so-doing evaluate the posterior probability with closer control for the tumor size distribution. For the subgroup analyses that compare the performance of RFA-GP on the small, medium and large tumor

subgroups we may estimate $\Pr(q_{\text{RFA}} < q_{\text{base}} \mid \text{size} = s, y_1, \dots, y_n, x_1, \dots, x_n)$ separately for each subgroup $s \in \{\text{small, medium, large}\}$.

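### SAP 6.4: the printed size mix and recurrence rates average 38.3% (lower limit about 0.361), not 24.1% and 0.2217; only the reversed mix gives the stated figures, and the documents do not show which is wrong

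*SAP*

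**What the plan says.** SAP section 6.4 takes size-specific rates from its reference [4]: "reoccurrence rates of 14.1%, 24.5%, and 58.1% were reported for the small, medium and large tumor groups". It then gives the mix expected in this trial, attributed to the clinic's experience: "The proportion of cases expected in the small, medium, and large categories are 12.9%, 41.9%, and 45.2% respectively". The benchmark for the overall comparison "is the weighted average of these proportions with the above recurrence rates, which equals 24.1" per cent.

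For precision the SAP states: "Because the failure rate data in [4] involve 1817 observations, we use this number as a basis for quantifying the precision in the baseline". The lower end of the 95% interval is given as q_base = 0.2217. The test is then framed for two thresholds: "For both the conservative and less conservative benchmarks, the overall assessment of the clinical success of PGP will be evaluated". The less conservative one is not defined; 24.1% is the natural reading.

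Section 6.4.6 builds its power statement on 0.2217: with 62 lesions and one-sided alpha of 0.05, power is 80% at a true recurrence of 0.105, a reduction of about 0.117. SAP section 6.2 treats clinical success as one of two primary outcomes. The protocol's Study Summary lists local recurrence under the secondary objective.

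**The concern.** The large-tumor group has by far the highest rate (58.1%) and, as printed, the largest share (45.2%). Those two numbers alone contribute more than 26 points, so the total cannot be 24.1%.

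q_base is the value against which recurrence under PGP is judged, and the 0.105 and 0.117 in section 6.4.6 depend on it. If the calculation is wrong, clinical success is tested against the wrong bar and the power statement does not describe the trial. If the list is wrong, the expected population is misdescribed: small tumors would be the largest group, not large ones.

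**Working it through.** **Inputs.** From SAP 6.4: rates 0.141, 0.245, 0.581; mix 0.129, 0.419, 0.452 (sum 1.000, equal to 8, 26 and 28 of 62 lesions); N = 1817. From SAP 6.4.6: 62 lesions, one-sided alpha 0.05, 80% power.

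**Step 1: benchmark from the printed inputs.** Sum of share × rate:
0.129 × 0.141 + 0.419 × 0.245 + 0.452 × 0.581 = 0.0182 + 0.1027 + 0.2626 = 0.3835.
Lower limit: 0.3835 − 1.96 × √(0.3835 × 0.6165 / 1817) = 0.3835 − 1.96 × 0.01141 = 0.3611.
Other interval choices (Wilson, one-sided 95%, stratified variance) give 0.361 to 0.365. None approaches 0.2217.

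**Step 2: all six orderings of the shares**, rates held in printed order, same lower-limit formula:

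| Small / medium / large share (%) | Average | Lower limit |
|---|---|---|
| 12.9 / 41.9 / 45.2 (printed) | 0.3835 | 0.3611 |
| 12.9 / 45.2 / 41.9 | 0.3724 | 0.3501 |
| 41.9 / 12.9 / 45.2 | 0.3533 | 0.3313 |
| 45.2 / 12.9 / 41.9 | 0.3388 | 0.3170 |
| 41.9 / 45.2 / 12.9 | 0.2448 | 0.2250 |
| 45.2 / 41.9 / 12.9 (reversed) | 0.2413 | 0.2217 |

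Only the full reversal gives both stated figures: 0.0637 + 0.1027 + 0.0749 = 0.2413, and 0.2413 − 1.96 × 0.01004 = 0.2217.

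**Step 3: reproduce section 6.4.6.** An exact one-sample binomial test with n = 62 and null value 0.2217 rejects at 8 or fewer recurrences (alpha 0.0483). Power at a true 0.105 is 0.801, and 0.2217 − 0.105 = 0.117. The power statement therefore follows from 0.2217.

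**Step 4: consequence if the printed mix is right and 0.2217 is kept.** Falls are measured from the lower limit, as section 6.4.6 does.
- False success at a true 0.3611: P(X ≤ 8) = 0.00004.
- 80% power still needs a true 0.105, a fall of 0.361 − 0.105 = 0.256.
- A fall of 11.7 points ends at 0.3611 − 0.117 = 0.2441. P(X ≤ 8) = 0.020. Against 24.1% (9 or fewer, alpha 0.0476) it is 0.042.

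**Step 5: the same branch with q_base corrected to 0.361.** The rule becomes 15 or fewer of 62 (alpha 0.0315). Power is 80% at a true 0.207, a reduction of 0.154. The same fall of 11.7 points, to 0.2441, succeeds with probability 0.55.

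**The case against.** The strongest reply is that this is a misprint in one sentence. The figures 24.1%, 0.2217, 0.105 and 0.117 agree with one another. The recurrence figures quoted from reference [5] also point that way: 25/110 (22.7%) in section 6.3, and about 26.4% at 2 years and 37.8% at 4 years in section 6.4. A benchmark of 38.3% would exceed even the 4-year figure, although the SAP says follow-up in [4] averaged less than 2 years. This has weight, and it leans towards a transposed list. It does not settle the matter: [5] is a different series with no stated size mix, and the internal agreement shows only that the four numbers come from one calculation.

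A second reply is that a strict threshold is safe. For false success that is correct. It does not answer the loss of power, and the SAP explains its conservatism by the confidence limit and the shorter follow-up in [4], not by a gap of 14 points.

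Two stronger readings are tempting and should be resisted. A reader might infer that 0.2217 is simply wrong; the documents leave both branches open. A reader might also take the 2% success rate as the full cost of the error. At a true 24.4% recurrence exceeds 0.2217, so the null hypothesis as stated is true there and a low rejection rate is automatic. The matching rate after correction is about 55%, not 80%, so correction alone would not restore the claimed power for 11.7 points. Nor does the SAP assume any relative reduction that could be carried over to a higher benchmark; it states only 0.105 and 0.117.

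**Conclusion.** The contradiction is certain: the stated benchmark and q_base cannot be obtained from the stated inputs. Provided the printed digits are right and only their order is at fault, the small and large shares were swapped either in the text or in the calculation.

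- **Reversed mix right:** the threshold and power figures stand, and only the printed proportions change.
- **Printed mix right:** the benchmark is 38.3% and q_base about 0.361. Keeping 0.2217 raises the fall needed for 80% power from 11.7 to 25.6 points. With q_base corrected, the detectable difference is about 0.154.

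Neither branch inflates false success.

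The power figures rest on the SAP's own illustrative exact test, unweighted, with 62 lesions. The actual criterion in section 6.4.4 is "The posterior probability of clinical success", with no stated cut-off. Assuming 0.95, complete 2-year data and a near-flat Beta prior, the limits are 8 of 62 for 0.2217 and 16 of 62 for 0.361, close to those above. Section 6.2 also says "we will weight our sample to equate to the relative frequencies of small, medium and large tumors" found in [4]. That weighting is not modelled here because the SAP does not give those frequencies.

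**What to change.** Before the clinical outcome is analysed, check the expected small/medium/large mix against the clinic data on which section 6.4 relies. Then:

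1. If the reversed mix is right, print the proportions as 45.2%, 41.9% and 12.9%, and leave 24.1%, 0.2217, 0.105 and 0.117 unchanged.
2. If the printed mix is right, and the clinic mix is the one that governs the benchmark, restate the benchmark as 38.3%, q_base as about 0.361, and section 6.4.6 as 80% power at about 0.207, a reduction of about 0.154.
3. If the weighting to [4] in section 6.2 governs instead, recompute the benchmark, q_base and the power statement on that mix.

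The cost is one check of an existing tabulation, followed by one corrected sentence or a short set of restated figures. No new patient data are needed.

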6.4.6 Power for clinical success

In lieu of performing an exact power calculation under the Bayesian model specified above, we will perform an illustrative calculation based on Fisher's exact test. Allowing a type I error of 0.05, the test of the above one-sided hypotheses for q_{RFA} with a sample-size of 62 lesions will reject the null hypothesis with 80% power if $q_{\text{RFA}} < 0.105$. That is, the minimal detectable difference is a reduction of approximately 0.117 in the likelihood of tumor reoccurrence – which is an effect size in line with conservative hypotheses about the improvement in outcomes that the PGP might introduce.

Subgroup analyses (e.g., based on treated tumor size) will require larger effect sizes to retain the same level of power. However, the study is only intended to be powered for the primary analysis.

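### The clinical benchmark q_base = 0.2217 puts a crude binomial error on a size-weighted rate. The correct error needs stratum counts that the SAP does not give, so the direction and size of the shift are unknown

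*SAP*

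**What the plan says.** SAP section 6.4 takes its size-specific rates from reference [4]: "reoccurrence rates of 14.1%, 24.5%, and 58.1% were reported for the small, medium and large tumor groups". It cautions: "However, these rates were evaluated over variable lengths of follow-up". The weights come from elsewhere: "The proportion of cases expected in the small, medium, and large categories are 12.9%, 41.9%, and 45.2% respectively (based on past clinical experience". The overall benchmark is "the weighted average of these proportions with the above recurrence rates, which equals 24.1" percent. On its precision the section says: "Because the failure rate data in [4] involve 1817 observations, we use this number as a basis for quantifying the precision in the baseline". The resulting lower 95% limit is q_base = 0.2217, presented as the most conservative comparison value. The section gives no variance formula and no breakdown of the 1817 by tumour size.

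The value is used in two places. Section 6.4.4 computes the posterior probability that the 2-year recurrence rate is below q_base. Section 6.4.6 gives an illustrative exact calculation with 62 lesions and one-sided alpha 0.05, which "will reject the null hypothesis with 80% power if" the true rate is below 0.105. Neither section states a cut-off in number of recurrences.

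**The concern.** A lower confidence limit needs the standard error of the estimate it is attached to. The 24.1% is not the proportion recurring among 1817 observations. It is a sum of three stratum rates with weights from outside [4]. Its precision depends on how many small, medium and large tumours lie behind each rate. A stratum that is thin in [4] but carries real weight in the benchmark makes the error larger than the binomial formula suggests. A size mix in [4] close to the weights makes it slightly smaller.

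The lower limit is one of the null values for a primary outcome, and the plan relies on it for part of its conservatism. The illustrative test also has little room: the rejection region implied by 0.2217 already has exact size 0.048.

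**Working it through.** **Inputs.** From section 6.4: rates p = 0.141, 0.245, 0.581 (small, medium, large); printed weights 0.129, 0.419, 0.452; total 1817. From section 6.4.6: n = 62, one-sided alpha 0.05, detectable rate 0.105. The stratum counts are not in the documents, so every split below is an assumption.

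**1. The point benchmark.**
- Printed weights: 0.129×14.1 + 0.419×24.5 + 0.452×58.1 = 1.82 + 10.27 + 26.26 = 38.3%.
- Small and large weights exchanged: 0.452×14.1 + 0.419×24.5 + 0.129×58.1 = 6.37 + 10.27 + 7.49 = 24.13%.

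Only the exchanged weights give the stated 24.1%. Steps 2 to 4 use them for that reason; step 5 returns to the printed weights.

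**2. The plan's limit reproduced.** Binomial SE = sqrt(0.24134×0.75866/1817) = 0.01004. Lower limit = 0.24134 − 1.96×0.01004 = 0.2217, as stated. This shows that the simple binomial error was used.

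**3. The limit with the stratified variance.** SE² = Σ w²p(1−p)/n. The numerators are:
- small: 0.452²×0.141×0.859 = 0.02475
- medium: 0.419²×0.245×0.755 = 0.03247
- large: 0.129²×0.581×0.419 = 0.00405

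For an assumed 60/35/5 split (1090, 636 and 91 lesions): SE = sqrt(0.0000227 + 0.0000511 + 0.0000446) = 0.0109, and the limit is 0.24134 − 1.96×0.01088 = 0.2200. The same steps for four splits give:

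| Assumed split S/M/L, % | SE | q_base | P(X ≤ 8 of 62) at q_base | Implied cut-off |
|---|---|---|---|---|
| 45/42/13 | 0.0095 | 0.2227 | 0.046 | 8 |
| 50/40/10 | 0.0097 | 0.2223 | 0.047 | 8 |
| 60/35/5 | 0.0109 | 0.2200 | 0.051 | 7 |
| 70/25/5 | 0.0116 | 0.2185 | 0.054 | 7 |

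The smallest SE that any split can give is Σ w·sqrt(p(1−p))/sqrt(1817) = 0.00941, so q_base cannot exceed 0.2229. On the low side these four splits set no bound. For example, 234/1348/234 lesions give SE 0.0121 and q_base 0.2176, although 12.9% of the tumours are large.

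**4. Effect on the illustrative test (exact binomial, n = 62).**
- At 0.2217: P(X ≤ 8) = 0.0483 and P(X ≤ 9) = 0.0930, so the implied cut-off is 8. Power at 0.105 is P(X ≤ 8) = 0.801, which matches section 6.4.6.
- P(X ≤ 8) reaches 0.05 at a null of about 0.2208. That needs SE = 0.01048, which is 4.4% above the binomial 0.01004 (about 9% in variance).
- With a cut-off of 7, power at 0.105 is P(X ≤ 7) = 0.676, and the rate detectable with 80% power is 0.091.

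**5. With the printed weights.** Binomial SE = sqrt(0.38346×0.61654/1817) = 0.0114, lower limit 0.361, implied cut-off 15. Over the four splits in the table the stratified SE is 0.0160, 0.0179, 0.0245 and 0.0249, so the binomial error is too small in each. The implied cut-off is 15, 15, 14 and 14.

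**The case against.** **The test is only illustrative.** No recurrence cut-off is written in the plan, and the planned analysis is Bayesian. This stands: 8 and 7 are implied by section 6.4.6 and are not decision rules. Much of the fall from 80% to 68% power also comes from the discreteness of an exact test. As a rough proxy for the Bayesian analysis, take a uniform prior and a 0.95 threshold (an assumption, since the SAP gives none). The posterior probability with 8 of 62 recurrences is then 0.957 at 0.2217, 0.955 at 0.2200 and 0.952 at 0.2185; nine recurrences fail at all three. The implied cut-off would not move. But q_base itself is not illustrative, because it enters the posterior probability in section 6.4.4.

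**The benchmark is deliberately conservative.** The SAP offers 1817 openly as a basis for precision, notes shorter average follow-up in [4], and tests against more than one value: "For both the conservative and less conservative benchmarks, the overall assessment of the clinical success of PGP will be evaluated using the hypothesis test". This limits the consequences. It does not make the binomial formula the error of a reweighted rate, and the follow-up argument is a separate source of margin.

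**The correct error may be smaller.** This also stands. If the size mix in [4] resembles the weights, q_base rises to 0.2227 and the implied cut-off stays at 8.

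**The weights are the larger problem.** Agreed, and they come first. The variance formula is still wrong under either order.

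A reader might infer that the cut-off really moves from 8 to 7, so that the trial is underpowered or its type I error inflated. The documents do not support that. They give no stratum counts, and two of the four assumed splits raise q_base. A size of 0.051 to 0.054 for the 8-recurrence rule arises only against a null lowered under an assumed split.

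**Conclusion.** The standard error behind q_base is the wrong one for the quantity described; given 24.13% and 1817, the arithmetic is right. The direction and size of the error cannot be determined from the documents. With the weights that reproduce 24.1%, the four assumed splits put q_base between 0.2185 and 0.2227, a shift of −0.0032 to +0.0010 from 0.2217; a more uneven size mix in [4] would lower it further. With the printed weights, the binomial error of 0.0114 compares with 0.016 to 0.025 over the same splits.

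The change in the illustrative test is conditional on q_base falling below about 0.2208 and is not established. This is a minor point: worth correcting because q_base is a null value for a primary outcome, but it does not by itself overturn the design.

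**What to change.** 1. Reconcile the printed size weights with the 24.1% benchmark in section 6.4, and state which size mix is intended. Section 6.2 speaks of weighting the sample to size frequencies for comparability with [4], while section 6.4 weights the benchmark to clinical experience. One statement should cover both.
2. Take the small, medium and large counts from [4] and state them in the SAP.
3. Recompute the lower limit as Σwp − 1.96·sqrt(Σ w²p(1−p)/n), with the reconciled weights, and show the formula.
4. Restate q_base in section 6.4, and the illustrative power and detectable rate in section 6.4.6, whichever way they move.

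The cost is one recalculation, provided [4] reports the counts behind its three rates. If it does not, the SAP should say so and show q_base over a stated range of splits. No trial procedure changes. The result may be slightly more or slightly less favourable to the device than 0.2217.

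### The clinical-success test is applied to two benchmarks (0.2217 and 24.1%) with neither named as decisive, and no posterior probability is set at which success is declared

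*SAP*

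**What the plan says.** SAP section 6.2 makes clinical success one of two primary outcomes, judged against a literature benchmark without a concurrent control. (The protocol's Study Summary lists local recurrence as a secondary objective; that difference is a separate matter.)

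Section 6.4 introduces two numbers.

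- It starts with "The benchmark number to be used for the overall group comparison", described as the "weighted average of these proportions with the above recurrence rates, which equals 24.1"%.
- It then takes the lower end of a 95% confidence interval, using 1817 historical observations, and sets q_base = 0.2217 "as our ideal or most conservative benchmark against which to compare outcomes under PGP".

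The test is then stated for the two together: "For both the conservative and less conservative benchmarks", overall clinical success is to be judged by testing H0: q_RFA ≥ q_base against H1: q_RFA < q_base.

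The planned analysis is Bayesian. Section 6.4.4 defines "The posterior probability of clinical success" as Pr(q_RFA < q_base | data) and explains how to compute it from posterior draws. It gives no value at which H0 is rejected.

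The only error rate for this endpoint is in section 6.4.6: "Allowing a type I error of 0.05, the test of the above one-sided hypotheses" with 62 lesions "will reject the null hypothesis with 80% power if" q_RFA is below 0.105. The SAP presents that calculation as illustrative, in place of one under the Bayesian model.

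**The concern.** A primary outcome needs one rule, fixed in advance, that turns the data into a yes or a no. Here two parts of the rule are open: which benchmark decides, and how large the posterior probability must be. No sentence ranks the benchmarks, requires both to be met, or labels one as supportive. The text also points in two directions: the symbol and the power figure to 0.2217, the sentence on the overall comparison to 24.1%.

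At stake is the SAP's own safeguard. The trial has one arm and a fixed historical comparator, and the SAP moves the benchmark to a confidence limit to allow for uncertainty in that comparator (section 6.4, with the same reasoning in 6.3 for technical success). If the point estimate can also support a success claim, and the choice can be made after the data are seen, the allowance no longer protects anything. Section 6.4 also lets clinical performance be estimated at any time once recruitment is over, which makes a fixed rule more important.

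**Working it through.** **Inputs.** n = 62 lesions (6.1, 6.4.6); benchmarks 0.2217 and 24.1% (6.4); one-sided 0.05 and target rate 0.105 (6.4.6); near-flat priors (6.4.3); 1817 historical observations, size-group rates of 14.1%, 24.5% and 58.1%, and weights of 12.9%, 41.9% and 45.2% (6.4).

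**Assumptions.** Lesions are independent, unweighted and fully followed for two years. The SAP's 0.05 is taken as the decision level, or 0.95 as its posterior counterpart.

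**1. Reproduce the SAP's power.** Use a one-sample exact binomial, lower tail, with X ~ Bin(62, q).

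- P(X ≤ 8 | 0.2217) = 0.0483 and P(X ≤ 9 | 0.2217) = 0.0930, so the rule is 8 or fewer recurrences.
- P(X ≤ 8 | 0.105) = 0.801.

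This matches the stated 80% power at 0.105. The stated difference also fits: 0.2217 − 0.105 = 0.1167, given as about 0.117. The power figure is therefore measured from 0.2217.

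**2. Same test against 24.1%.**

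- P(X ≤ 9 | 0.241) = 0.0476 and P(X ≤ 10 | 0.241) = 0.0897, so the rule is 9 or fewer.
- P(X ≤ 9 | 0.105) = 0.889.

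**3. Posterior version.** With complete data and near-flat priors, q_RFA is approximately Beta(x, 62 − x). Tumour size drops out because βx_i is common to all five categories in the model of 6.4.2.

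| Recurrences | Exact p vs 0.2217 | Exact p vs 0.241 | Pr(q < 0.2217) | Pr(q < 0.241) |
|---|---|---|---|---|
| 8/62 | 0.048 | 0.023 | 0.974 | 0.989 |
| 9/62 | 0.093 | 0.048 | 0.945 | 0.974 |
| 10/62 | 0.160 | 0.090 | 0.896 | 0.946 |

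At 0.05 or 0.95, 8/62 meets both benchmarks, 9/62 meets only 24.1%, and 10/62 meets neither.

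**4. Other decision rules.** The count that meets only the easier benchmark moves but does not vanish.

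| Rule | Split at | vs 0.2217 | vs 0.241 |
|---|---|---|---|
| Posterior cut-off 0.90 | 10 | 0.896 | 0.946 |
| Posterior cut-off 0.975 | 8 | 0.974 | 0.989 |
| Score z test, 0.05 | 9 | 0.073 | 0.039 |
| Wald test, 0.05 | 10 | 0.098 | 0.044 |
| Continuity-corrected z test, 0.05 | 8 | 0.054 | 0.028 |

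**5. Error rates.** At a true rate of 0.2217, success is declared with probability 4.8% under ≤8/62 and 9.3% under ≤9/62. At a true rate of 24.1%, the ≤9/62 rule has error 4.8%.

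**6. The benchmark itself.**

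- As stated: 0.129 × 0.141 + 0.419 × 0.245 + 0.452 × 0.581 = 0.0182 + 0.1027 + 0.2626 = 0.383.
- With the small and large weights exchanged: 0.452 × 0.141 + 0.419 × 0.245 + 0.129 × 0.581 = 0.0637 + 0.1027 + 0.0749 = 0.2413. Its lower limit is 0.2413 − 1.96 × √(0.2413 × 0.7587 / 1817) = 0.2217.

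So 24.1% and 0.2217 agree with each other but not with the weights as printed. If 38.3% were right, the same formula gives a lower limit of 36.1%. The exact 0.05 rules would then be ≤17/62 and ≤15/62, so 9/62 would pass both and the split would move to 16 and 17.

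**The case against.** The strongest reply is that the SAP does have a lead benchmark. The symbol q_base is given one value, 0.2217. The hypotheses and the posterior probability are written in that symbol, and power is measured from it. Section 6.3 takes the same conservative approach for technical success. On this reading, 24.1% is a step on the way to q_base and is merely reported alongside it. That is a reasonable inference and supports choosing 0.2217 in the fix. It does not settle the matter, because 6.4 names 24.1% as the number for the overall comparison and then applies the test to both values. Even if 0.2217 is accepted, the posterior cut-off is still missing.

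A reader might infer three stronger things that the documents do not support.

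- *That 9/62 would be both a success and a failure.* The tests are nested: rejecting at 0.2217 implies rejecting at 24.1%. A result of 9/62 would be shown to lie below the point estimate but not below its lower limit.
- *That the SAP allows success on either benchmark, so its error rate is 9.3%.* The SAP states no such rule. If both had to be met, the error at 0.2217 would stay at 4.8%. The 9.3% applies only if 24.1% alone decides and the true rate equals the deliberately lowered limit.
- *That 9/62 is a fixed feature of the plan.* It depends on the assumed cut-off. Section 6.2 plans size weighting and 6.1 expects about 30% of patients to contribute two tumours, so a raw count need not determine the planned result.

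**Conclusion.** The point holds as an unspecified decision rule for an outcome that the SAP calls primary: two benchmarks without a ranking, and a posterior probability without a threshold. Every decision rule tried leaves a count that meets 24.1% but not 0.2217. It is 9/62 under one-sided 0.05 or a 0.95 posterior cut-off, and 8 or 10 under others, for independent, unweighted, fully followed lesions.

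What could be lost is the buffer for benchmark uncertainty: 9.3% instead of 4.8% at a true rate of 0.2217 if the easier benchmark alone were enough, with the error against 24.1% still 4.8%. These figures also assume that 24.1% and 0.2217 survive reconciliation with the stated weights and rates. If they do not, the counts change but the missing rule remains. The point should be corrected; it does not show that the planned test is invalid.

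**What to change.** First reconcile the benchmark with the stated weights and rates, which as written give 38.3% and not 24.1%.

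Then add a rule to 6.4.4, for example: clinical success is declared only if Pr(q_RFA < q_base | data) > 0.95, where q_base is the lower 95% confidence limit of the reconciled benchmark (0.2217 if 24.1% stands) and the probability comes from the planned size-weighted analysis. The comparison with the point-estimate benchmark is a sensitivity analysis and supports no success claim.

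The rule itself costs one sentence. If 0.2217 stands, the power stated in 6.4.6 is unchanged, since in the unweighted, complete-data case the rule is ≤8/62 (posterior 0.974 at 8, 0.945 at 9). If the benchmark changes, the critical count and the power must be recalculated. The downside for the sponsor is that success can no longer be claimed on the easier benchmark alone.
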